6.3 Withdrawal criteria

Parent(s) or legal representative(s) are free to withdraw the subject from the study at any time, without prejudice to continued care.

Subjects **must** be withdrawn from the study if any of the following occur:

1. The Sponsor or a regulatory agency requests withdrawal of the subject.
2. Parent(s) or legal representative(s) withdraw their consent for the subject to participate.
3. Subject is treated with prohibited concomitant medications as defined in this protocol.
- 4a. Subject has direct (conjugated) bilirubin levels $>2\text{mg/dL}$.
5. Subject requires phototherapy or exchange transfusion due to elevation of total bilirubin.
- 6a. Subject has AST, ALT or ALP values $3\times$ ULN, with the following exception:

For subjects with perinatal asphyxia, elevation of AST, ALT or ALP $<5\times$ ULN is acceptable for continuation in the study, if initial and peak elevation of LFTs occurs within 5 days after birth, and if the time course of LFT elevation is compatible with hepatic injury due to perinatal asphyxia (ie, peak LFT elevation within a few days after birth, and subsequent normalization until up to day 14 after birth).

In case AST, ALT or ALP elevation $\geq 5\times$ ULN occurs within 5 days after birth, study drug must be discontinued and LFTs retested within 24 hours. If AST, ALT and ALP are confirmed to be $<5\times$ ULN, the subject may restart study drug after consultation with and approval by the Medical Monitor.

The determination of ULN will be based on the subject's GA and the site's normal range values for the respective GA.

Subjects **may** be withdrawn from the study if any of the following events occur:

- 7a. Subject experiences prolongation of seizure duration, a worsening of seizure burden, or emergence of new seizure type considered by the Investigator to require intervention.
8. Investigator may withdraw subject due to any medical condition, based on clinical judgment and discretion.
- 9a. Subject has AST, ALT or ALP values between $>2\times$ and $\leq 3\times$ ULN, with the following exception:

For subjects with perinatal asphyxia, elevation of AST, ALT or ALP <5 x ULN is acceptable for continuation in the study, if initial and peak LFT elevation occurs within 5 days after birth, and if the time course of LFT elevation is compatible with hepatic injury due to perinatal asphyxia (ie, peak LFT elevation within a few days after birth, and subsequent normalization until up to day 14 after birth).

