3 DATA ANALYSIS CONSIDERATIONS

3.1 General presentation of summaries and analyses

Statistical analysis and generation of tables, figures, subject data listings, and statistical output will be carried out using SAS® Version 9.3 or higher.

Descriptive statistics, such as the number of subjects with available measurement (n), mean, standard deviation (SD), median, minimum value, and maximum value for quantitative variables, and counts and percentages for categorical variables, will be provided. Confidence intervals (95% CIs) will be provided for efficacy variables.

Unless otherwise noted, denominator for percentages will generally be based on the set of subjects with at least 1 assessment at the time point or at least 1 assessment during the time interval being summarized.

Decimal places for descriptive statistics will always apply the following rules:

- “n” will be an integer.
- Mean, SD and median will use 1 additional decimal place compared to the original data.
- Minimum and maximum will have the same number of decimal places as the original value.

Unless otherwise noted, all percentages will be displayed to 1 decimal place. No percentage will be displayed for zero counts, and no decimal will be presented when the percentage is 100%.

In general, descriptive summaries will be used to present study results overall (for the Confirmatory Cohorts) and by cohorts (Exploratory Cohort and each individual Confirmatory Cohort).

Subject data listings will be provided and will present source data and key derived variables for statistical analyses.

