4.2 Handling of dropouts or missing data

There will be no specific imputation of missing data except for missing dates and/or times for concomitant medication and AE.

The handling of missing dates and times for seizures if applicable will be discussed during the Data Evaluation Meeting (DEM).

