4.6 Use of an efficacy subset of subjects

The efficacy analysis will be based on the FAS subjects from the Confirmatory Cohorts.

The efficacy evaluation at the end of the Down-Titration Period will be based on the subset of subjects in the Confirmatory Cohorts who enter the Down-Titration Period.

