5 STUDY POPULATION CHARACTERISTICS

5.1 Subject disposition

The number of screen failures and the primary reason for screen failure will be summarized for all enrolled subjects (ie, all subjects with the signed informed consent).

Disposition of subjects screened will be summarized overall and by sites: the date of first subject in, date of last subject out (latest scheduled or unscheduled visit), and the number of enrolled subjects will be summarized for all study sites and by study site. Additionally, the number of subjects in each of the SS, FAS and PK-PPS will be summarized overall and by cohorts.

Disposition and Discontinuation Reasons by Periods

- Subjects started study
- Subjects entered treatment
- Subjects completed study
- Subjects discontinuing the study and primary reason for discontinuation
- Subjects started Screening Period
- Subjects completed Screening Period
- Subjects discontinuing the study during the Screening Period and primary reason for discontinuation
- Subjects started Evaluation Period
- Subjects completed Evaluation Period
- Subjects discontinuing the Evaluation Period and primary reason for discontinuation
- Subjects entering BRV Extension Period
- Subjects switching to Oral Solution prior to entering the BRV Extension Period
- Subjects completed BRV Extension Period
- Subjects qualifying to enter the Long-Term Follow-up study
- Subjects discontinuing during the BRV Extension Period and primary reason for discontinuation
- Subjects entering Safety Follow-Up Period and not entering BRV Extension Period
- Subjects entering Down-Titration Period and not entering BRV Extension Period (Confirmatory Cohorts)
- Subjects completed Down-Titration Period (Confirmatory Cohorts)
- Subjects discontinuing during the Down-Titration Period and primary reason for discontinuation (Confirmatory Cohorts)
- Subjects entering Safety Follow-Up Period after completing Down-Titration Period (Confirmatory Cohorts)

All percentages will be relative to the number of enrolled subjects.

Discontinuation due to Adverse Events

A summary of discontinuations due to AEs for the SS will present the number and percentage of subjects who discontinued this study due to AEs overall, and by type of AE.

Listings of study eligibility criteria text, of subjects who did not meet study eligibility criteria, of subject disposition and of subject analysis sets will be provided for all subjects screened.

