8.2.3 Sensitivity analysis of the main secondary efficacy variable

The impact of missing data on the assessment of the main secondary efficacy variable will be evaluated with sensitivity analyses. Subjects who drop out for reasons other than due to lack of

BRV efficacy, are switched over to another AED treatment, or are administered any rescue medication (including BZDs) will be excluded from the analysis.

The numerator of the main secondary efficacy variable is defined as the number of responders to BRV treatment from Baseline to 3 hours after the initial BRV dose (see [Section 8.1](#) for the definition of BRV responders). Subjects, who dropped out for reasons other than due to lack of BRV efficacy, are switched over to another AED treatment or received any rescue medication during the first 3 hours after the initiation of BRV treatment will be excluded from the analysis.

The denominator is defined as the number of the FAS subjects in the Confirmatory Cohorts with the following subjects excluded: subjects who dropped out for reasons other than due to the lack of BRV efficacy reasons, are switched to another AED or received any rescue medication (including BZDs) during the first 3 hours after the initiation of BRV treatment.

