- Proportion of subjects who are seizure-free (100% reduction in seizure burden from Baseline, i.e. those subjects whose seizure burden disappeared) at 24 hours following the start of initial BRV treatment, categorized by subjects with non-severe or severe seizure burden at Baseline [**derivations**: the numerator is the number of subjects with 100% reduction in seizure burden from Baseline or no ENS during the last 2 hours of the 24-hour time period following the start of initial BRV treatment, see the definition of baseline seizure burden in [Section 8.1](#), the denominator is defined as the number of subjects in the FAS from Confirmatory Cohorts.]
- Time to reduction in seizure burden for BRV responders (defined as the first time point when BRV responder criteria are met) [**derivations**: the time to reduction in seizure burden is measured in hours, defined as the first time point (date and time) when BRV responder criteria are met minus the date and time of the first BRV dose, event is defined as response to BRV, subjects will be evaluated for response at the following time points: 3 hours, 4 hours, 5 hours, etc., 96 hours after the initial BRV dose. Response will be calculated referring to the last 1 hour prior to the time point. Non-responder for the analysis of other than main efficacy variable subjects defined in the [Section 8.1](#) are censored with time to censoring defined as the date and time of the event defining the non-responder status (drop out due to lack of BRV efficacy, switch over to another AED treatment, used >1 dose of rescue medication following the first 3 hours after initiation of BRV treatment) or date and time of the end of the Evaluation Period in case there are no events of response or non-response minus the date and time of first BRV dose; when the time is not collected, use HH:MM=23:59.]
- Seizure freedom at the end of the Down-Titration Period (Confirmatory Cohorts only) [**derivations**: defined as proportion of subjects who are seizure-free at the end of the Down-Titration Period, the numerator is the number of subjects with seizure-freedom defined as no ENS at the end of the Down-Titration Period, i.e. no ENS during 1 hour of VEEG, the denominator is defined as the number of subjects in the FAS from Confirmatory cohorts with VEEG data at the end of the Down-Titration Period.]

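### Seizure freedom at the end of Down-Titration drops babies lost to death or seizures from its denominator instead of counting them as not seizure-free

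*SAP*

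**What the plan says.** Seizure freedom at the end of Down-Titration is a listed secondary efficacy variable (Protocol 4.2.1, SAP 2.2.2.1). In SAP 8.2.4 a baby counts as seizure-free with "no ENS during 1 hour of VEEG", and the denominator is "the number of subjects in the FAS from Confirmatory cohorts with VEEG data at the end of the Down-Titration Period". SAP 4.6 describes the population differently: the evaluation "will be based on the subset of subjects in the Confirmatory Cohorts who enter the Down-Titration Period", with no VEEG condition.

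Protocol 8.2.4 places this recording, of at least an hour, on the last day of the taper. It is planned for babies who discontinue brivaracetam during the Evaluation Period, who do not go on to the Extension Period, or who leave the Extension Period without entering the long-term study. Footnote i of Protocol Table 5-3 limits the recording to babies who complete the study after the Evaluation Period.

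For missing data, SAP 4.2 states: "There will be no specific imputation of missing data except for missing dates and/or times for concomitant medication and AE". SAP 3.1 adds a general default, unless otherwise noted: the "denominator for percentages will generally be based on the set of subjects with at least 1 assessment at the time point". The planned check is confined to another variable: "The impact of missing data on the assessment of the main secondary efficacy variable will be evaluated with sensitivity analyses" (SAP 8.2.3).

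**The concern.** The denominator depends on having the measurement, and the reasons for lacking it can be the outcome itself. Protocol 6.3 lets the investigator withdraw a baby when "Subject experiences prolongation of seizure duration, a worsening of seizure burden, or emergence of new seizure type" is judged to need intervention. A withdrawn baby goes to the Safety Follow-Up visit (Table 5-3, footnote b), where no VEEG is scheduled. Death is an anticipated serious event in babies with hypoxic-ischemic encephalopathy (Protocol 11.1.1.2.1). The SAP expects some losses in this period, because SAP 5.1 tabulates discontinuations during Down-Titration by reason.

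This is the only efficacy variable tied to the end of the brivaracetam taper. If babies lost to seizures or death are left out, the reported rate describes the babies who could be measured, not those who began the taper.

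**Working it through.** **Does another rule put these babies back?**

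- Imputation: none for efficacy data (SAP 4.2).
- Non-responder rules (SAP 4.2.3 and 8.1.1): these classify response to brivaracetam, not seizure freedom at the end of the taper.
- Sensitivity analysis (SAP 8.2.3): main secondary variable only.
- Sibling variables (SAP 8.2.4): seizure freedom at 24 hours and by time interval both use the whole Confirmatory FAS. A baby without data there stays in the denominator and cannot enter the numerator.

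So nothing returns the lost babies, and this variable departs from the SAP's own treatment of seizure freedom.

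**Inputs.** The documents give no expected rate, no number entering Down-Titration and no drop-out rate, so there is no planned figure to reproduce. All counts below are assumed.

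**Formulas.** Let N be the babies entering, n those with a VEEG at the end, x the seizure-free among those n, and m = (N − n)/N the missing share.

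- Rate under SAP 8.2.4: x/n.
- Rate if every missing baby is a failure: x/N = (x/n)(1 − m).
- Inflation in that case: 1/(1 − m), which is 1/0.9 = 1.11 at 10% missing, 1/0.8 = 1.25 at 20%, 1/0.7 = 1.43 at 30% and 1/0.6 = 1.67 at 40%.

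With 12, 20 or 36 entrants, about 10% to 40% missing, and about 50% to 70% of the measured babies seizure-free, the gap x/n − x/N runs from about 5 to about 30 percentage points.

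**Example: N = 20, n = 14, x = 10** (exact 95% intervals)

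| Handling of the 6 babies without a VEEG | Rate |
|---|---|
| Left out (SAP 8.2.4) | 10/14 = 71.4% (41.9 to 91.6) |
| All counted as not seizure-free | 10/20 = 50.0% (27.2 to 72.8) |
| All counted as seizure-free | 16/20 = 80.0% |

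**Direction.** If a fraction q of the 6 missing babies are seizure-free, the rate among all entrants is (10 + 6q)/20. It equals 71.4% when q = 10/14 = 71.4%. At q = 0.5 it is 13/20 = 65%, so SAP 8.2.4 overstates. At q = 0.9 it is 15.4/20 = 77%, so SAP 8.2.4 understates. The sign depends on who is missing.

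**Separating the reasons.** Suppose 4 of the 6 were lost to death, seizures or lack of efficacy, and 2 had no VEEG for other reasons. Counting the 4 as failures and setting the 2 aside gives 10/(14 + 4) = 10/18 = 55.6%, with 2 not assessed. Dividing by all 20 gives 50.0%, which treats the 2 unmeasured babies as failures.

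**The case against.** A reader might infer that a baby reaches the denominator only by completing the taper. The documents do not support that. SAP 3.2.2.2.5 ends the period at the last brivaracetam administration, the taper may be shortened, and Protocol 8.2.4 allows extra VEEGs during it. A baby whose seizures return and who is recorded on the last dosing day counts, and counts as a failure. SAP 3.2.3 also maps early-discontinuation assessments to matching scheduled visits. That helps little here, because the VEEG time points it names belong to the Evaluation Period. Withdrawal for worsening seizures is optional, so recurrence does not by itself remove a baby.

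A reader might also infer that the reported rate can only equal or exceed the rate among all entrants. That does not follow. Under footnote i, babies who taper after the Extension Period may have no recording planned. They entered it because they were judged to benefit, so losing them could pull the rate down. For the same reason, dividing by every entrant would count babies unmeasured by design as failures.

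The two SAP passages can be reconciled by reading 4.6 as the population and 8.2.4 as the denominator within it, in line with the SAP 3.1 default. That reading is fair. It settles the wording but leaves the lost failures uncounted.

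Losses are also visible elsewhere: discontinuations by reason (SAP 5.1), deaths by period (SAP 10.2.1) and adverse events during the taper (SAP 10.4.11). The variable is descriptive, with no test or decision rule (SAP 4.5). These points limit the weight of the concern. They do not change the rate that will be reported.

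**Conclusion.** The concern holds in a limited form. Followed as written, SAP 8.2.4 drops babies who die, or who are withdrawn or stop the taper for seizures or lack of efficacy, when they have no VEEG on the last brivaracetam day. Nothing else in the plan counts them as not seizure-free, and SAP 4.6 names a wider population.

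If such losses are 10% or 20% of entrants and are the only ones, the rate is inflated by a factor of 1.11 or 1.25. Both shares are assumptions. The net bias is likely upward, because death and seizure-related loss are unfavourable outcomes, but it is not proven while some babies may lack a VEEG by design. This is a cheap, worthwhile correction to one descriptive secondary variable and does not affect the main secondary efficacy result.

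**What to change.** 1. In SAP 8.2.4, define the denominator as Confirmatory FAS babies who enter Down-Titration and either have a VEEG at its end, or have none because they died, were withdrawn or discontinued the taper for seizures or lack of efficacy. Count the second group as not seizure-free.
2. Report babies with no VEEG for any other reason, including those for whom none was planned, as not assessed, with the reason, outside the denominator.
3. Keep the rate among babies with a VEEG as a supportive line.
4. Align SAP 4.6 with this definition.
5. Reconcile Protocol Table 5-3 footnote i with Protocol 5.1.2 and 8.2.4, so that it is clear which babies are due the recording.

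The analysis change uses data already collected and costs SAP wording only. Item 5 also needs a clarification in the protocol. The downside is that the reported rate may be less favourable.

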8.2.5 Analysis of the secondary efficacy variables

Categorical secondary efficacy variables will be summarized using descriptive statistics (counts and proportions with the 95% CIs). Continuous key efficacy variables will be analyzed descriptively as described in [Section 3.1](#).

Time to reduction in seizure burden will be summarized descriptively by individual Confirmatory Cohorts and for all combined Confirmatory Cohorts, the cumulative number of events (response to BRV), Kaplan-Meier estimates at each hour during the Evaluation Period and median time to seizure burden reduction with 95% confidence interval will be provided. Also, graphical displays of Kaplan-Meier curves will be provided for each cohort separately.

A listing of secondary efficacy variables will be provided for the FAS.

8.3 Statistical analysis of other efficacy variables

8.3.1 Derivations of other efficacy variables

The other efficacy variables are defined as follows:

- Absolute and percentage reduction from Baseline in seizure burden at evaluation periods of 0 hours to 3 hours, >3 hours to 6 hours, >6 hours to 12 hours, >12 hours to 24 hours, >24 hours to 36 hours, >36 hours to 48 hours, >48 hours to 72 hours, and >72 hours to 96 hours after the start of initial BRV treatment [*derivations*: see the definition of baseline seizure burden and of average per hour seizure burden in [Section 8.1](#), the **absolute reduction** is defined as the difference between the baseline average per hour seizure burden and average per hour seizure burden at evaluation periods of 0 hours to 3 hours, >3 hours to 6 hours, >6 hours to 12 hours, >12 hours to 24 hours, >24 hours to 36 hours, >36 hours to 48 hours, >48 hours to 72 hours, and >72 hours to 96 hours after the start of initial BRV treatment. The **percentage reduction** is defined as the absolute reduction in seizure burden divided by the baseline average per hour seizure burden and multiplied by 100.]
- Categorized percentage reduction from Baseline to the end of the 96-hour Evaluation Period in seizure burden (<-25% [worsening], -25% to <25% [no change], 25% to ≤50%, 50% to <80%, and ≥80%) [*Derivations*: The **percentage reduction** of seizure burden is defined as the difference between the average per hour baseline seizure burden and the average per hour seizure burden at the end of the 96-hour Evaluation Period divided by the average per hour baseline seizure burden and multiplied by 100. For the definition of the average per hour seizure burden, please see [Section 8.1](#).]
- Proportion of BRV responders by time interval at evaluation periods of 0 hours to 3 hours, >3 hours to 6 hours, >6 hours to 12 hours, >12 hours to 24 hours, >24 hours to 36 hours, >36 hours to 48 hours, >48 hours to 72 hours, and >72 hours to 96 hours after the start of initial BRV treatment [*derivations*: see the definition of BRV responders in [Section 8.1](#), for the numerator calculate the number of responders during the given above evaluation periods 0-3 hours, >3-6 hours, >6-12 hours, >12-24 hours, >24-36 hours, etc., the denominator is defined as the number of subjects in the FAS from Confirmatory Cohorts.]
- Proportion of subjects who are switched over from BRV to another AED during the 96-hour Evaluation Period [*derivations*: for the numerator calculate the number of subjects who stopped iv BRV and started another AED during the Evaluation Period, the denominator is defined as the number of subjects in the FAS from Confirmatory Cohorts.]
- Proportion of responders to other treatment during the 96-hour Evaluation Period (including at the end of the 96-hour Evaluation Period, and by time intervals: 0 hours to 3 hours, >3 hours to 6 hours, >6 hours to 12 hours, >12 hours to 24 hours, >24 hours to 36 hours, >36 hours to 48 hours, >48 hours to 72 hours, and >72 hours to 96 hours after the start of initial BRV treatment. [*Derivations*: only subjects who switched from BRV to other treatment (stopped BRV due to lack of efficacy) during the 96-hour Evaluation Period will be considered for this variable. See the definition of **responder to other treatment** in [Section 8.1](#). The numerator for proportion of responders to other treatment at the end of 96-hour Evaluation Period is the number of responders to other treatment as defined in [Section 8.1](#); the denominator is the number of subjects in FAS from Confirmatory Cohorts. The numerator for proportion of responders to other treatment during the time intervals: 0-3 hours, >3-6 hours, >6-12 hours, >12-24 hours, >24-36 hours, >36-48 hours, >48-72 hours, >72-96 hours after the start of initial BRV treatment is defined as the number of responders to other treatment with the other treatment stop date and time during 0-3 hours, >3-6 hours,

>6-12 hours, ..., >48-72 hours, >72-96 hours after the start of initial BRV treatment respectively. The denominator is the number of subjects in FAS from Confirmatory Cohorts.]

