2.4 Determination of sample size

At least 42 evaluable subjects will be enrolled in this study, with at least 6 subjects in the Exploratory Cohort and at least 36 subjects will be enrolled in 3 successive Confirmatory Cohorts, each consisting of 12 subjects. At least 2 subjects undergoing hypothermia treatment will be included in the Exploratory Cohort and each of the 3 Confirmatory Cohorts.

Subjects in the Exploratory Cohort might be replaced due to lack of data, as deemed necessary following the review of PK and safety data by the DMC.

No formal sample size calculation has been performed as a single treatment BRV arm is planned for descriptive summary results and for comparison with the 6 subjects from the Exploratory Cohort. The total number of at least 36 subjects in the Confirmatory Cohorts is expected to provide sufficient evidence of tolerability, safety, and efficacy, as well as good precision for the PK profile of BRV in neonates.

Confirmatory Cohort subjects who drop out or are withdrawn from study participation will not be replaced.

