4.5 Multiple comparisons/multiplicity

Not applicable for this study. The study is not statistically powered, and all analyses are of descriptive nature. No statistical tests will be performed.

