8.1.6 Responder to other treatment

Responder to other treatment is defined as subject who stopped BRV or switched from BRV to act as a rescue medication and achieved at least 80% reduction (≥ 80 percent change) in non-severe seizure burden from start of other treatment to end of other treatment or at least 50% reduction (≥ 50 percent change) in severe seizure burden measured from initiation of other treatment to end of other treatment during the 96-hour Evaluation Period. Baseline Period for other treatment is defined as 1 hour prior to starting the other treatment. Other treatment Evaluation Period is from the start to the end of other treatment or to the end of 96-hour Evaluation Period if other treatment end is after the 96-hour Evaluation Period.

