8.3.2 Analysis of other efficacy variables

Categorical other efficacy variables will be analyzed using descriptive statistics (counts and proportions with the 95% CIs). Continuous key efficacy variables will be analyzed descriptively as described in [Section 3.1](#).

A listing of other efficacy variables will be provided for the FAS.

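### The proportion responding to other treatment counts only babies switched from BRV but divides by the whole Confirmatory FAS, so it is not a response rate among those switched

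*SAP*

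**What the plan says.** SAP 8.1.6 limits who can qualify: "Responder to other treatment is defined as subject who stopped BRV or switched from BRV to act as a rescue medication" and then met the 80% or 50% reduction threshold on that treatment. SAP 8.3.1 narrows this for the proportion itself: "only subjects who switched from BRV to other treatment (stopped BRV due to lack of efficacy) during the 96-hour Evaluation Period will be considered" for the variable. The same derivation then states that "the denominator is the number of subjects in FAS from Confirmatory Cohorts". It says this once for the end of the 96-hour Evaluation Period and again for the time intervals.

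For the intervals, a responder is placed according to when the other treatment stopped.

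The proportion who switch is a separate variable over the same FAS denominator: "for the numerator calculate the number of subjects who stopped iv BRV and started another AED during the Evaluation Period". It does not require that BRV was stopped for lack of efficacy.

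Protocol 4.2.2, 10.2 and 13.5.2 name the variable and define the responder but give no denominator. SAP 8.3.2 provides counts, proportions and 95% CIs.

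**The concern.** A response rate needs a denominator of subjects who could have responded. Here a baby who stays on BRV cannot be a responder to other treatment, yet counts as one who did not respond. The sentence limiting the variable to switched subjects and the sentence setting the denominator describe different populations.

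Two consequences follow. First, the figure moves with the number of babies who leave BRV as well as with how well the other treatment works. With the same response among switched babies, fewer switches give a lower reported rate. Second, the confidence interval looks tighter than it should, because its sample size includes babies who did not switch.

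At stake is the meaning of one table. A reader taking its title at face value would understate response among switched babies by an amount the title does not reveal.

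**Working it through.** The plan states no expected switch proportion, response rate or dilution factor, so there is no figure of its own to reproduce.

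**Inputs**
- N, the Confirmatory FAS size. SAP 2.4 says "at least 36 subjects will be enrolled in 3 successive Confirmatory Cohorts, each consisting of 12 subjects", so 36 stands in for N. The actual FAS may be smaller.
- S, the number who switch under the numerator's criterion, and s = S/N. Not in the documents, so assumed and shown as a range.
- x, the responders among those S. Also assumed.
- 95% confidence level, from SAP 3.1 and 8.3.2. The SAP sections on these proportions name no interval method; exact (Clopper-Pearson) limits are used here.

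**Formulas**
- Rate under the SAP rule: x/N.
- Rate among switched subjects: x/S.
- Ratio: (x/S) ÷ (x/N) = N/S = 1/s, whatever the response rate.
- Since x cannot exceed S, the SAP rate cannot exceed S/N = s, even if every switched baby responds.

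**Ratio over the assumed range of s**

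| s | 10% | 16.7% | 25% | 33.3% | 50% | 66.7% | 83.3% | 100% |
|---|---|---|---|---|---|---|---|---|
| 1/s | 10 | 6.0 | 4.0 | 3.0 | 2.0 | 1.5 | 1.2 | 1.0 |

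**Illustration with N = 36 and an assumed 50% response among switched subjects**

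| S | x | SAP rule, x/36 (95% CI) | Among switched, x/S (95% CI) |
|---|---|---|---|
| 6 | 3 | 8.3% (1.8 to 22.5) | 50.0% (11.8 to 88.2) |
| 12 | 6 | 16.7% (6.4 to 32.8) | 50.0% (21.1 to 78.9) |
| 18 | 9 | 25.0% (12.1 to 42.2) | 50.0% (26.0 to 74.0) |
| 24 | 12 | 33.3% (18.6 to 51.0) | 50.0% (29.1 to 70.9) |
| 36 | 18 | 50.0% (32.9 to 67.1) | 50.0% (32.9 to 67.1) |

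Response among switched babies is the same in every row, yet the SAP figure runs from 8.3% to 50.0%.

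**One further assumed case**

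If 10 of 36 switch and 6 respond, the SAP rule gives 6/36 = 16.7% (6.4 to 32.8). Among those switched it is 6/10 = 60.0% (26.2 to 87.8). The ratio is 36/10 = 3.6. The SAP figure could not exceed 10/36 = 27.8%. The interval widths are 32.8 − 6.4 = 26.4 points and 87.8 − 26.2 = 61.6 points.

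**Interval rule**

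The interval numerator needs a stop time of the other treatment within the interval, and the last interval ends at 96 hours. SAP 8.1.6 allows the other treatment to run past 96 hours and truncates its evaluation there. A responder still on it at that point has no stop time inside any interval and so is counted in none, whichever denominator is used.

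**The case against.** The strongest defence is that the planned figure is a coherent quantity: the share of all FAS subjects who switched and then responded. On that reading, the sentence about switched subjects only says who may enter the numerator. The FAS denominator is stated twice and matches the neighbouring proportions in 8.3.1. Where the SAP wants a subset denominator it says so, as for baseline severity groups and end-of-down-titration VEEG in 8.2.4. The protocol sets no denominator, so the SAP does not depart from it. All this shows that the denominator was chosen on purpose. It does not make the figure fit the variable's name or the sentence restricting who is considered.

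A second defence is that the information can be recovered, since counts, the switch proportion and subject listings are all planned. This holds only in part. The switch variable counts any stop of iv BRV with another AED started, so its count is not the matching denominator when some stops had other reasons. The listings would help, but the planned CI would still be for a different quantity.

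A third defence is low impact, and it stands. This is an other efficacy variable, and SAP 4.5 says that "The study is not statistically powered, and all analyses are of descriptive nature". No decision rule uses it.

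A reader might go further and infer that other AEDs are set against BRV on unequal terms. It is true that every FAS subject received BRV, while only some switched. However, no planned analysis compares the two rates. The only planned efficacy comparison sets the main secondary variable against published historical rates (Protocol 13.5.1, SAP 8.2.2).

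**Conclusion.** The point holds as a mismatch between numerator and denominator. Followed as written, SAP 8.3.1 reports the proportion of the FAS who switched and responded, under a name that promises a response rate to other treatment.

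The understatement is 1/s and rests only on the switch proportion. A reader might infer that the rate is necessarily diluted several-fold, but the documents do not support that because they give no switch proportion. The factor reaches 3 only if one third or fewer of the FAS switch (12 or fewer of 36). It is 2 or less if half or more do, and there is none if all do. The 16.7% against 60.0% example is one assumed case within that range.

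The consequence is confined to one descriptive variable and its intervals. No conclusion about BRV changes.

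**What to change.** In SAP 8.3.1:

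1. Settle one switching criterion. SAP 8.1.6 admits subjects who stopped or switched, while 8.3.1 requires stopping for lack of efficacy. Use the same wording in both.
2. For the 96-hour figure, use as denominator the Confirmatory FAS subjects who meet that criterion, and report x/S with its 95% CI.
3. For each interval, use the switched subjects whose other treatment is assessed in that interval. State how subjects still on other treatment at 96 hours are assigned, since the numerator currently depends on a stop time.
4. Keep the FAS-based figure only if it is labelled as the proportion of all FAS subjects who switched and responded. Continue to report the switch proportion separately.

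The cost is SAP wording and the matching table specification, with no new data. The one drawback is a wider CI on fewer subjects, which reflects how few babies inform the rate.
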